#### A. Patient Population

##### **Sample size, age, gender, race, ethnicity, clinical status**

##### **1. Vanguard**

We will enroll 36 patients (16 AA and 20 H/L) that represent our study sites' geographic, health system and practice size diversity. Each site will be asked to recruit a specific Race or Ethnicity for this small pilot based on the predominant Ethnic/Racial group at that site. 18-75 years old without regard to gender. Race/ethnicity assignment will be based on self-identification. For patients who self-identify in both categories, they will be randomized as H/L since studies on asthma in H/L include those patients as such. Based on our past experience, more than 70% will be female. We also expect that almost half will be active smokers or have a significant smoking history. Broadly, these patients will have asthma and be at risk for exacerbations. They either will have been prescribed ICS/LABA or if taking ICS without LABA will still have symptoms or have had an exacerbation in the past year. In our BELT study looking at use of long-acting bronchodilators, among >1,000 AA patients that we recruited who were either symptomatic on ICS or taking ICS+LABA, more than one- third had an exacerbation, of which 80% went to the emergency room.

##### **2. Full Study**

Full study difference: We will enroll up to 1210 patients: 605 AAs and 605 H/Ls.

##### **3. Participant subgroups (Full study only)**

The subgroups of the total study population to be analyzed are AAs, H/Ls, smokers and non-smokers. Regarding AAs and H/Ls, the barriers to success of PARTICS may vary in the different racial/ethnic groups. In fact, in one PARTICS-type study, H/L appeared to benefit less from a PARTICS approach (Calhoun 2012). Therefore, we will perform a subgroup analysis in which we analyze AA and H/L separately using the definitions above regarding race/ethnicity assignment. Regarding smoking, according to the CDC's 2010 Behavioral Risk Factor Surveillance System, about 21% of people with asthma are active cigarette smokers (CDC 2010). Active smokers are well known to have increased asthma morbidity compared with non-smokers (Lange 1998, Marquette 1992, Polosa 2013, Shavit 2007, Sippel 1999, Siroux 2000). More importantly, active smokers have a decreased therapeutic response to ICS as measured by asthma control scores, FEV1, and airway reactivity (Pederson 1996, Chalmers 2002, Lazarus 2007). Further, a study showed that this reduced therapeutic response to corticosteroids also occurs in former smokers with a greater than 10 pack-year smoking history (Chaudhuri 2003). In that study, both active smokers and former smokers had reduced FEV1, daytime symptom, and rescue medication use responses to corticosteroids as compared with those who smoke less than 10 pack-years. We will analyze current (within one year) or former smokers (> 10 pack-years) vs. non-smokers (no smoking within 1 year and <10 pack-years). We know that initial patient screening in BELT eliminated 40-50% of the patients who appeared qualified based on current or prior (>10 pack-year smoking history). Thus, we expect that 40-50% of the patients in our current, pragmatic study will be current or former smokers.

Additional subgroups will include patients with high FeNO vs. low and Eosinophil count high vs. low. Regarding the FeNO subgroups measurement of FeNO at baseline, FeNO is a good marker of type 2 inflammation (Silkoff 2017). Type 2 inflammation is (i) driven by type 2 helper T and innate lymphoid cells, (ii) through the actions of the cellular mediators interleukins 4, 5, and 13, (iii) which results among other effects in eosinophil infiltration (Fahy 2015). FeNO is associated with all three of these features of type 2 inflammation. It correlates with the presence of the cellular drivers of type 2 inflammation (Liu 2015), and with high expression levels of interleukins 4, 5, and 13 (Peters 2014). FeNO also correlates with eosinophil infiltration as detected through the several ways of sampling for airway inflammation, including sputum (Gibson 2000), bronchoalveolar lavage fluid (Warke 2002), and bronchial biopsies (Ricciardolo 2012). Knowing that ICS therapy is particularly effective at targeting type 2 inflammation, and that FeNO is a marker of type 2 inflammation, it is not surprising that FeNO is also a marker of responsiveness to ICS therapy, as noted by the American Thoracic Society (Dweik 2011).

We will conduct a binary analysis with pre-specified thresholds (20 ppm and 30 ppm). In addition, we will conduct ROC analysis to identify optimal threshold for sensitivity and specificity. These analyses will be conducted in relation to our primary outcome (exacerbations) and our secondary outcomes. We will examine these outcomes in our intent-to-treat and our per-protocol populations. We will also test for heterogeneity based on race/ethnic status, smoking status, and additional factors enumerated in our primary protocol

Peripheral blood eosinophils identify asthmatics that are most responsive to Patient Activated Reliever-Triggered Inhaled CorticoSteroid (PARTICS). The PARTICS approach utilizes a patient-centric, provider-friendly approach to using inhaled corticosteroids. Inhaled corticosteroids (ICS) are the most effective medications for the treatment of asthma (Adams 2005, GINA guidelines 2014). The PARTICS approach relies on the fact that asthma is responsive to ICS (Haahtela 1991). Evolving data suggest that while the majority of asthma patients respond to ICS (Martin 2007), a significant minority might not (Woodruff 2009). It

appears that the majority that responds has a type of inflammation that is closely associated with eosinophils and is labeled Type 2 inflammation (Fahy 2015, Peters 2014). While this area is evolving, a recent review has suggested that blood eosinophils may be one of the best biomarkers to identify patients likely to respond to ICS or therapies directed at Type 2 patients (Pavord 2017). There has been enthusiasm about blood eosinophils since the sample is easily obtainable and the assay is available in ANY clinical laboratory. We will determine whether peripheral blood eosinophil count serves as an effect modifier of the relationship between treatment (PARTICS vs. usual care) and the study's primary outcome (number of asthma exacerbations per year). We will stratify participants based on a pre-specified peripheral blood eosinophil count threshold of 300/uL. This threshold is based on a frequently-used cutoff for 'eosinophil-high' status in the anti-eosinophil therapy literature (Giannetti 2016).

As discussed in section **III.E, Biostatistical analysis**, we will be adequately powered for both these subgroup analyses.

Additional exploratory subgroup will be considered including the following factors: 1) modality in which questionnaires have been returned; 2) patients' attitude towards ICS from the validated BMQ (skeptical (low necessity, high concerns), indifferent (low necessity, low concerns), ambivalent (high necessity, high concerns), accepting (high necessity, low concerns)); 3) presence of depressive symptoms (yes/no); 4) health literacy status (low or marginal versus high); and 5) Discrimination stressors from the everyday discrimination scale (SHORT).

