## **4. FeNO**

Fractional exhaled nitric oxide (FeNO): Exhaled nitric oxide gas will be measured during the study visit. Asthma is an inflammatory disease of the lung. The PREPARE trial relies on the fact that in many cases asthmatic inflammation is of the eosinophilic (or Type 2) form of inflammation.

Corticosteroids are particularly effective in targeting Type 2 inflammation. While inhaled corticosteroids (ICS) were initially thought to be a therapy for all asthmatics, studies now suggest that up to half of asthmatics may have non-type 2 inflammation and thus may be less responsive to ICS (Woodruff 2009). Thus, it is possible that PARTICS may be most beneficial for a particular group of patients – those with Type 2 mechanisms of inflammation.

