## 6. Subgroup Analysis

Subgroup analyses for the primary efficacy outcome will be performed on the ITT population in order to explore whether the treatment effect is consistent across subgroups. Our goal is to determine the impact of PARTICS on asthma exacerbations in two pre-specified main subgroups determined by 1) race/ethnic group (African American vs. Hispanic/Latino) and 2) smoking status [i.e., participants who are previous (>10 pack- years)/current (or within 1 year) smokers vs. those who have not smoked (in the past year and <10py)] 3) patients with high FeNO vs. low and 4) patients with high eosinophil counts vs. low. Based on our prior experience, about 50% of our population will be smokers or ex- smokers.

Subgroup analyses to evaluate variation in treatment effect will be performed on the basis of tests for interaction using the same Andersen-Gill version of the Cox proportional hazards model as used in the primary analysis. The model will be including terms for treatment arm, subgroup, and treatment by sub-group interaction and adjust for all variables included in the primary model. Additionally, treatment effects within each categorical subgroup will be examined separately using analogous Andersen-Gill model. Event rates by treatment arm and hazard ratios with 95% confidence intervals will be reported for each subgroup. Forest plots will be generated displaying the estimated hazard ratios and 95% confidence intervals for each subgroup will be presented. Variation in treatment effect will be assessed on the basis of tests for interaction in the Andersen-Gill version of the Cox proportional hazards model described above. Treatment effects estimated within each categorical subgroup will be considered exploratory/hypothesis generating. Thus, no adjustment for multiple testing will be employed.

Additional exploratory subgroup analyses will be performed investigating the effect of the following factors: 1) modality in which questionnaires have been returned; 2) patients' attitude towards ICS from the validated BMQ (skeptical (low necessity, high concerns), indifferent (low necessity, low concerns), ambivalent (high necessity, high concerns), accepting (high necessity, low concerns)); 3) presence of depressive symptoms (yes/no); 4) health literacy status (low or marginal versus high); and 5) patient adherence barriers from the validated ASK12 questions 1,2,3 and 11 related to measures of inconvenience, forgetting and

cost.

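### The FeNO ROC would find a prognostic threshold rather than a threshold for PARTICS benefit, and the FeNO interaction test has no named cut (minor)

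*Combined protocol and SAP*

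**What the plan says.** Section III.C.4 (FeNO) gives the reason for measuring the marker: corticosteroids act mainly on type 2 inflammation. "Thus, it is possible that PARTICS may be most beneficial for a particular group of patients", it says, meaning those with that mechanism.

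Section III.E.6 (Subgroup Analysis) sets the test. "Subgroup analyses for the primary efficacy outcome will be performed on the ITT population", by a treatment-by-subgroup interaction in the Andersen-Gill model, with a forest plot. The listed subgroups include "3) patients with high FeNO vs. low and 4) patients with high eosinophil counts vs. low". No FeNO value is given there or in III.C.4.

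The only numbers are in section II, Participant subgroups (Full study only): "We will conduct a binary analysis with pre-specified thresholds (20 ppm and 30 ppm"). Neither threshold is ranked above the other. The text continues: "In addition, we will conduct ROC analysis to identify optimal threshold for sensitivity and specificity". It then says "These analyses will be conducted in relation to our primary outcome (exacerbations) and our secondary outcomes" and "We will examine these outcomes in our intent-to-treat and our per-protocol populations".

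For eosinophils, the same section fixes one cut: "We will stratify participants based on a pre-specified peripheral blood eosinophil count threshold of 300/uL".

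**The concern.** The question is about effect modification: does the treatment hazard ratio change with FeNO? Model, outcome and population for that question are fixed in III.E.6. Two things are not in order.

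**The ROC answers a different question.** Sensitivity and specificity for exacerbation describe how well FeNO separates patients who have events from those who do not. That is prognosis. The analysis yields an optimal threshold even if PARTICS works equally well at every FeNO level. The plan also does not say how a recurrent, censored count becomes a yes/no outcome, whether high or low FeNO is the positive test, or whether the arms are pooled.

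**The interaction test has no governing cut.** With two unranked thresholds, the choice of which result goes in the forest plot and the text can be made after both have been seen.

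At stake is the reading of one exploratory biomarker result. A threshold printed beside the interaction results could be taken as the FeNO level above which PARTICS works.

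**Working it through.** **Inputs from section III.E.8.** Control rate 0.4 per year; 15 months (1.25 years) of follow-up; 31.25% uniform loss over that time; 600 per arm; two-sided 0.05; a 32% reduction as the subgroup effect.

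**Reproducing the plan's power.** Mean exposure = 1.25 × (1 − 0.3125/2) = 1.0547 years. Control events = 600 × 1.0547 × 0.4 = 253.1. For a 23.5% reduction, SE of the log rate ratio = √(1/253.1 + 1/(0.765 × 253.1)) = 0.0955, z = 0.2679/0.0955 = 2.81, and power = Φ(2.81 − 1.96) = 80.1%. The plan states 80%.

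**Interaction power at one cut.** Assume a 32% reduction above the cut, none below, and every patient measured. With share p above the cut, h = 253.1p and l = 253.1(1 − p) control events:

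var = 1/h + 1/(0.68h) + 2/l, and z = 0.3857/√var

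- p = 0.5: var 0.0353, z 2.05, power 53.7%
- p = 0.3: var 0.0438, z 1.84, power 45.3%
- p = 0.2: var 0.0587, z 1.59, power 35.7%

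**Two nested cuts.** The documents give no FeNO distribution, so the shares above the lower and upper cut (p1, p2) are assumed. The two test statistics correlate at about r = √[p2(1 − p1)/(p1(1 − p2))]. If the true step is at one cut, the expected z at the other is r times as large. Bivariate normal results:

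| Shares above lower/upper cut | r | No modification: any of two p<0.05 | No modification: exactly one | Step at lower cut: power lower/upper; disagree | Step at upper cut: power lower/upper; disagree |
|---|---|---|---|---|---|
| 50/30% | 0.655 | 8.5% | 7.1% | 53.7/26.9%; 34.2% | 22.6/45.3%; 30.9% |
| 60/35% | 0.599 | 8.8% | 7.5% | 52.9/23.0%; 37.1% | 21.1/48.7%; 35.2% |
| 40/20% | 0.612 | 8.7% | 7.4% | 51.2/23.0%; 35.7% | 16.4/35.7%; 27.8% |

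A different assumption (lognormal FeNO, geometric SD 2, median 15–30) gives about 8.7% for any of two, with 18–23% of patients lying between 20 and 30 and so changing group.

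**ROC against outcome.** One version had to be chosen: arms pooled, outcome any exacerbation yes/no, cut maximising sensitivity plus specificity, 2,000 simulated trials of 1,200 with the III.E.8 rate and loss.

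- FeNO prognostic (assumed rate ratio 1.35 per SD), no modification: AUC 0.60. With an assumed median of 20 and geometric SD 2, the ROC cut has a 5th–95th percentile range of about 15–31. A fairly stable cut appears although there is no benefit threshold to find.
- FeNO not prognostic, 32% benefit only in the top 30%: AUC 0.48. With high FeNO as the positive test, the cut is within 10 percentile points of the benefit cut in 3% of trials (2% and 5–6% if the benefiting share is 50% or 20%). If the direction is set by the data, it is 47%.
- Both together: AUC 0.57, below the 0.60 for prognosis alone, and within 10 points in 12–13% of trials.

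The ROC cut follows prognosis and coding. A real benefit in high-FeNO patients lowers their event rate in one arm, and so weakens the signal that the ROC uses.

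**The case against.** The strongest reply is that this is exploratory work and the plan says so. FeNO is in none of the stated aims, which name race/ethnicity and smoking. III.E.6 calls within-subgroup effects hypothesis generating and makes no multiplicity adjustment. Two thresholds fixed in advance and both reported with confidence intervals are a legitimate form of pre-specification. The added error is also modest. Four independent interaction tests already carry 1 − 0.95⁴ = 18.5% risk of any positive, and a second FeNO cut raises this to about 1 − 0.95³ × (1 − 0.087) = 21.7%. All of that stands, and it is why the point is minor. It does not settle which split enters the interaction test and forest plot, because the exploratory label is attached to within-subgroup effects.

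A reader might infer that the two cuts could give opposite answers. The figures do not show that. They measure disagreement on p<0.05 only. In simulation, when one test was significant and the other was not, both estimates pointed the same way in 95–98% of cases, and significant results in opposite directions occurred in at most 0.005% of trials.

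A reader might also infer that the ROC cut will be carried into the interaction model. No section says so.

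The ROC percentages describe one assumed version of an analysis that the plan leaves open. The argument that an outcome ROC measures prognosis does not depend on that version.

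**Conclusion.** The concern holds in two limited parts. The outcome ROC cannot locate a threshold for PARTICS benefit, and this follows from what sensitivity and specificity measure. The FeNO interaction test lacks a governing cut, and this follows from the text alone. The sizes (8.5–8.8% against 5%; 28–37% disagreement on p<0.05; 3–13% for the ROC with high FeNO positive and benefit in the top 30%) rest on assumed marker shares, an assumed 32%-versus-0% contrast, an assumed prognostic strength and complete FeNO measurement.

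Severity is minor. The primary conclusion is untouched. It would be tempting to extend the criticism to eosinophils, but they already have one cut and an interaction test, so no change is needed there. Nor do the figures support a general claim that a continuous FeNO term is more powerful. At a 50/50 split it gives 73% against 54% if modification is linear, and 37% against 54% if it is a step at the cut. The case for it is that it addresses the question asked.

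**What to change.** Before any results by arm are seen:

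1. Replace the ROC with the treatment hazard ratio as a function of continuous log(FeNO), from a treatment-by-log(FeNO) term in the same Andersen-Gill model, reported as supplementary. It should not replace or rescue the binary test; if either could count, type I error would be about 8%. If the ROC is kept, label it prognostic, state its yes/no outcome, the direction of a positive test and the handling of arm, and do not use its cut in the interaction test.
2. Name one of the two stated thresholds for the III.E.6 interaction test and forest plot, and report the other as a sensitivity analysis.

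The cost is SAP wording and a few lines of code on data already collected, with no change to sample size. The downside is that the named cut may be the less informative one: power is 16–27% if the true step is at the other cut, against 36–54% at the true one. The sensitivity analysis may point to this but could not overturn the governing test.

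### The only FeNO cut-offs in the plan are written in parts per million, almost certainly a slip for parts per billion; applied literally, they would leave the high-FeNO subgroup empty.

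*Combined protocol and SAP*

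**What the plan says.** Section II, Participant subgroups (Full study only), introduces two biomarker subgroups: "Additional subgroups will include patients with high FeNO vs. low and Eosinophil count high vs. low". For FeNO it then says "We will conduct a binary analysis with pre-specified thresholds (20 ppm and 30 ppm", and adds "In addition, we will conduct ROC analysis to identify optimal threshold for sensitivity and specificity". It applies these analyses to the primary and secondary outcomes, in both the intention-to-treat and per-protocol populations.

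III.E.6 Subgroup Analysis lists "3) patients with high FeNO vs. low and 4) patients with high eosinophil counts vs. low" after race/ethnicity and smoking, without restating a FeNO threshold. The model for each subgroup is specified there: "The model will be including terms for treatment arm, subgroup, and treatment by sub-group interaction and adjust for all variables included in the primary model". Hazard ratios within each subgroup level and forest plots are also planned.

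On the measurement, III.C.4 FeNO says only "Exhaled nitric oxide gas will be measured during the study visit". The full-study overview in II.B, the FeNO test description in II.D.5 and VII.B.4 Procedural Risks describe the procedure but give no unit, device range or cut-off. The abbreviation ppb does not occur in the documents.

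**The concern.** A pre-specified threshold settles, before anyone sees the data, who counts as high. Here the only written threshold carries a unit that does not fit the quantity. If it is programmed as written, one level of the subgroup has no patients and the planned interaction test has nothing to compare. If the analyst silently uses a different unit, the analysis will work, but the threshold applied will differ from the one on record, in an open-label trial. The companion biomarker shows what was needed: the eosinophil cut-off of 300/uL is given with a usable unit both in Participant subgroups and in III.C.5.

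**Working it through.** The cut-offs are a stated definition, so there is no derived figure to reproduce. The check is a unit conversion, followed by the share of patients that each reading would class as high.

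**Inputs from the documents.** Cut-offs of 20 ppm and 30 ppm (Participant subgroups); planned enrolment of up to 1,210 ("We will enroll up to 1210 patients: 605 AAs and 605 H/Ls").

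**Assumptions, not in the documents.** FeNO is read in ppb, from single digits to a few hundred. For the shares, FeNO is taken as log-normal with median m from 15 to 40 ppb and geometric SD g from 1.8 to 2.5.

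**Step 1, conversion.** 1 ppm = 1,000 ppb, so 20 ppm = 20 × 1,000 = 20,000 ppb and 30 ppm = 30 × 1,000 = 30,000 ppb.

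**Step 2, share above a cut-off t.** Share = 1 − Φ[(ln t − ln m) / ln g].

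| Cut-off read as | Lowest share in the range | Highest share in the range |
|---|---|---|
| 20 ppb | 0.312 (m = 15, g = 1.8) | 0.881 (m = 40, g = 1.8) |
| 30 ppb | 0.119 (m = 15, g = 1.8) | 0.688 (m = 40, g = 1.8) |
| 20,000 ppb | effectively 0 | 5.9 × 10⁻¹² (m = 40, g = 2.5) |
| 30,000 ppb | effectively 0 | 2.5 × 10⁻¹³ (m = 40, g = 2.5) |

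For example, at m = 15, g = 1.8 and t = 20: (ln 20 − ln 15) / ln 1.8 = 0.288 / 0.588 = 0.489, and 1 − Φ(0.489) = 0.312.

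**Step 3, expected count under the literal reading.** In the most favourable case, 1,210 × 5.9 × 10⁻¹² is about 7 × 10⁻⁹ patients above the lower cut-off. That is zero for any practical purpose, and the exact distribution does not matter: a single high patient would need a reading of at least 20,000 ppb.

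**Step 4, what would be lost.** With no patients in the high group, the subgroup term and the interaction term in the Andersen-Gill model are not identified, and there are no data for a high-group hazard ratio. The low-group hazard ratio can still be estimated; it is simply the treatment effect in everyone with a FeNO reading.

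**Consistency with the plan's own rationale.** III.C.4 says that as many as half of people with asthma may lack type 2 inflammation, which leaves about half or more who have it. Participant subgroups presents FeNO as a good marker of that inflammation. A cut-off that classes nobody as high contradicts this reasoning, whereas 20 and 30 ppb populate both groups.

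**The case against.** The strongest reply is that nothing would go wrong in practice. If the device reports ppb, an analyst would compare the readings with 20 and 30 directly and get a workable split. Anyone who did program 20,000 would see an empty group at the first tabulation. This largely stands, and it is why the point is minor.

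It can also be said that the ppb scale appears nowhere in the documents. That is true, and it is treated here as an assumption. It is the basic scale of the measurement rather than a result taken from a cited study, and the conclusion holds across the whole range shown.

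The reach is narrow as well. The ROC analysis sets its own threshold; the eosinophil subgroup and the primary analysis in III.E.4 do not use FeNO cut-offs. III.E.6 treats effects within subgroups as exploratory, and Specific Aim 2 covers only race/ethnicity and smoking.

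A reader might infer that the FeNO subgroup analysis is bound to fail, or that no hazard ratio within a FeNO group could be estimated. The documents support neither. The first depends on a literal application that is unlikely. The second is too broad, because the low-group hazard ratio survives even then.

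What remains is that the sole written definition of the subgroup is wrong, and no other passage corrects it.

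**Conclusion.** The text is wrong as written, and the severity is minor. Assuming FeNO is read in ppb, the stated cut-offs are too high by a factor of 1,000, almost certainly through a unit slip. Under a literal reading the high-FeNO group in III.E.6 has an expected count of zero among 1,210 patients, and the treatment-by-FeNO interaction and the high-group hazard ratio cannot be estimated. The same literal cut-offs would leave the high group empty in the FeNO analyses of secondary outcomes and of the per-protocol population. The slip is no ground for doubting the primary analysis or any other subgroup.

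**What to change.** In Section II, Participant subgroups (Full study only), change the two cut-offs from 20 ppm and 30 ppm to 20 ppb and 30 ppb. In III.E.6, where the plan lists only "patients with high FeNO vs. low", repeat the cut-offs with their unit so that the subgroup is defined where it is analysed. The cost is a two-word correction and one added phrase. No data collection, sample size or other analysis changes, and because FeNO serves only to classify patients for analysis, patient care is not affected.

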#### **6. Blood draw (Eosinophils):**

During the enrollment visit, we will ask each participant if s/he agrees to have blood drawn.

The blood draw is to determine Eosinophil counts which are known to be associated with response to Inhaled Corticosteroids. The test used will be a complete blood count with differential (CBC with differential). The amount of blood needed for this test is 3 mL, collected in a purple top tube. This will be the only blood draw for the participant throughout the study. This procedure will only be conducted during the full study.

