## **8. Sample Size and Power Considerations**

Sample size and power calculations were performed using PASS software (Hintze 2011), using the similarity of inference between the Andersen-Gill models and Poisson regression.

For the primary efficacy outcome, power calculations were based on an estimated primary event intensity of 0.4 per year (0.5 per 15 months) in the control arm (as seen in the BELT study), 15 months of follow-up for each individuals with an annualized rate of uniform loss to follow-up of 25% (31.25% in 15 months of follow-up) and a two-sided significance level of 0.05. With these assumptions, 1200 up to patients (600 per arm) yields 80% power to declare a reduction of 23.5% in the intensity of exacerbations as statistically significant. Even if the event rate were lower at .35 we would still have 80% power to detect a 25% difference. This difference is clinically meaningful and is well within the 25-50% (and more likely 40-50%) (O'Byrne 2006, Rabe 2006, Buhl 2012, Papi 2013, Calhoun 2012) reductions noted with such studies.

For subgroup analysis, using these same assumptions, with group size of 600 (300/arm), at a power level of 80% we would be able to detect an expected change of 32%, still well within the noted effects.

Power for secondary outcome comparisons were also calculated. Based on results observed in the BELT study, we expect the standard deviations in ASUI scores to be 0.23 in each arm. Thus, we will have 80% power to detect a difference of 0.04 in ASUI scores between treatment arms. Assuming standard deviations of 4.9 in each treatment arm on the ACT questions score, we will have 80% power to detect a difference of 0.96 in ACT scores.

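### Effect modification by blood eosinophils (and FeNO) is tested only through cut-points; adding a continuous biomarker-by-treatment interaction would be a cheap efficiency gain unless the effect truly steps at the cut

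*Combined protocol and SAP*

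**What the plan says.** The combined protocol and SAP puts the question in two places, the section on participant subgroups for the full study and Section III.C.5: does eosinophil count modify the treatment effect on exacerbations? The method is a single cut: "We will stratify participants based on a pre-specified peripheral blood eosinophil count threshold of 300/uL". The reason given is that this value is in common use in studies of anti-eosinophil drugs.

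For FeNO the subgroup section says "We will conduct a binary analysis with pre-specified thresholds", namely 20 and 30, and adds a ROC analysis to look for a best threshold.

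Section III.E.6 carries both markers into the analysis as FeNO high versus low and "patients with high eosinophil counts vs. low". Each is tested by a treatment-by-subgroup term in the Andersen-Gill model used for the primary outcome. It does not say which FeNO cut defines high. Section III.E.7 lists further interactions with treatment (BMI, ICS/LABA use, comorbidity, prior exacerbations), but neither biomarker.

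Blood is optional. Section II.D.6 says "we will ask each participant if s/he agrees to have blood drawn", and no expected number of samples is given.

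**The concern.** Both markers are measured on a continuous scale. A split at 300/uL treats counts of 20 and 299 as alike and counts of 299 and 301 as opposites. If benefit changes gradually with the count, this discards information in an interaction test, which is already much less precise than a test of the main effect.

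The power section covers only the effect inside a subgroup of 600, not the difference between subgroups, so nothing in the plan shows that the interaction test has precision to spare. What is at stake is the chance of recognising that PARTICS works better in some patients than in others. The primary comparison is not at stake.

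**Working it through.** **Inputs from Section III.E.8.** "a two-sided significance level of 0.05"; "estimated primary event intensity of 0.4 per year (0.5 per 15 months) in the control arm"; "annualized rate of uniform loss to follow-up of 25% (31.25% in 15 months of follow-up"); and ("600 per arm) yields 80% power to declare a reduction of 23.5% in the intensity of exacerbations". Allocation is 1:1.

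**Step 1: reproduce the plan's figures.** With uniform loss, mean exposure is 1.25 × (1 − 0.3125/2) = 1.055 years. Expected control events are 600 × 1.055 × 0.4 = 253. Expected PARTICS events are 253 × 0.765 = 194, so the total is D ≈ 447. SE of the log rate ratio = √(1/253 + 1/194) = 0.0955. Then |ln 0.765|/0.0955 = 2.81, and power = Φ(2.81 − 1.96) = 80%. This matches the plan. For 300 per arm and a 32% reduction the same formula gives 79%, against a stated 80%.

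**Step 2: precision of the planned interaction test.** If a share p of events lies above the cut, SE = √(4/(pD) + 4/((1−p)D)).
- p = 0.50: SE = 0.189. 80% power needs a ratio of hazard ratios of exp(−2.80 × 0.189) = 0.59. Power for a ratio of 0.70 is 47%.
- p = 0.25: SE = 0.219. 80% power needs a ratio of 0.54. Power for a ratio of 0.70 is 37%.

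**Step 3: cost of the split under a log-linear modifier.** Assume the log hazard ratio is linear in a normally distributed (log) marker. The efficiency of a split relative to the linear term is φ(c)²/(p(1−p)), where c is the cut in SD units and p the share of patients above it. The documents do not give p, so a range is shown. The last two columns give the power of the split where the continuous term has 80%. The simulations use 1200-patient Poisson trials with robust SE, 1500 runs each.

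| Share above cut | Efficiency | Information lost | Split power, closed form | Split power, simulated |
|---|---|---|---|---|
| 50% | 0.637 | 36% | 60.9% | 60% |
| 35% | 0.603 | 40% | 58.5% | 55% |
| 30% | 0.576 | 42% | 56.6% | not run |
| 25% | 0.539 | 46% | 53.9% | 48% |
| 20% | 0.490 | 51% | 50.0% | 44% |

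Simulated information losses at shares of 50%, 35%, 25% and 20% were about 37%, 44%, 53% and 58%.

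**Step 4: a worked gradient.** Assume 0.25 in log hazard ratio per SD and 28% above the cut (both assumed). Continuous term: SE = 2/√447 = 0.0946, z = 0.25/0.0946 = 2.64, power = Φ(2.64 − 1.96) = 75%. Split: efficiency 0.562, z = 2.64 × √0.562 = 1.98, power = Φ(0.02) = 51%. Simulation of the same case gave 75% and 48%. If only 800 patients had a count (assumed), D = 447 × 800/1200 = 298, and closed-form power is 58% against 37%. With overdispersion (assumed gamma variance of 1) and 1200 measured, simulated power is 61% against 37%.

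**Step 5: a true step at the cut.** With half the patients above the cut and a ratio of hazard ratios of 0.588, simulated power is 78% for the split and 59% for the continuous term. With 30% above and a ratio of 0.561, it is 72% and 48%.

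**The case against.** The case for leaving the plan alone has several parts.

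- **The loss is conditional.** A reader might infer that the split always discards about 40% of the information. It does so only for a gradual modifier and for certain shares above 300/uL. With a step at the cut the ranking reverses (Step 5). This stands.
- **The rationale does not favour a gradient.** A reader might think the type 2 inflammation argument predicts a gradual relation. The text does not say so. The subgroup section and Section III.C.4 speak of patients who respond and a group who may not, which is closer to two classes. This stands, although a noisy marker of class membership can still produce a smooth gradient, and the 300/uL value comes from a different drug class.
- **The consequence is easily overstated.** A reader might conclude that real modification would probably be missed and a consistent effect wrongly reported. At full sample the split detects the worked gradient about half the time. Section III.E.6 reports hazard ratios with intervals in each subgroup, calls the within-subgroup estimates exploratory, and nowhere says that a non-significant interaction will be reported as consistency. This stands.
- **These are additional subgroups.** Specific Aim 2 covers only race/ethnicity and smoking. The eosinophil cut is single and fixed in advance, so it carries no data-driven cut-point bias. Both points are right.
- **The FeNO ROC analysis uses the whole range.** True, but it ends in another threshold and is not a test of interaction.
- **The worked gradient is large.** Around the design rate ratio of 0.765 it implies hazard ratios of about 0.60 at +1 SD and 0.98 at −1 SD. At 0.15 per SD, power is about 35% continuous and 22% split, both inadequate.

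None of this supplies a continuous test, or a reason in the documents to expect a step at the chosen cut.

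**Conclusion.** The point holds as an efficiency improvement to additional subgroup analyses. Eosinophils and FeNO are tested as effect modifiers only through cut-points. Under a log-linear modifier on a normal scale, a single split loses about 36% to 51% of the information for shares above the cut of 50% to 20%. For a gradient of 0.25 per SD, power is about 50% rather than 75%. These figures rest on the assumed shape, gradient and share, and on the plan's roughly 447 events coming from patients who all have a count.

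The documents do not support a fixed 40% loss, a prediction of a gradual relation, or a forecast that the trial will report a false consistency. No stated figure is wrong: the plan's power calculations reproduce.

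**What to change.** In Section III.E.6, add treatment by continuous log(eosinophil count) and treatment by log(FeNO), each with its main effect and the primary-model covariates, in the same Andersen-Gill model. Name these as the pre-specified main interaction tests for the two markers. State in advance how zero counts enter the log. Plot the estimated hazard ratio with its confidence interval across the observed range. Keep the 300/uL and FeNO split estimates in the forest plot, and report the number of patients with each measurement.

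The cost is SAP wording, settled before results by arm are seen. No new data, patients or procedures are needed, and every planned split estimate is kept. The downside is lower power if the effect truly steps at the cut. The change narrows the power gap but does not by itself make these interaction tests adequately powered, and the SAP should say so.
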